1.0 Background

Dementia is an increasingly prevalent, costly and burdensome condition. The dramatic aging of the US population is creating a dementia "epidemic" that our health care system is poorly prepared to handle. More than 5 million people are affected by Alzheimer's disease (AD) and related dementias in 2016, with that number estimated to nearly triple to 13.8 million by 2050. The direct health care costs alone for dementia care are projected to increase from \$236 billion in 2016 to more than \$1 trillion in 2050. In addition to cognitive and functional deterioration, patients with dementia experience behavioral and psychological complications such as agitation and depression. Family caregivers of patients with dementia experience higher levels of anxiety, depression, chronic fatigue, and an increased mortality risk.

Dementia and palliative care are national research priorities. Both dementia and palliative care have been identified as priority conditions for research and quality improvement by numerous organizations such as the Institute of Medicine, National Quality Forum, the Centers for Medicare and Medicaid Services, and Agency for Healthcare Research and Quality and NIA. In addition, a workgroup developing milestones for care and support under the U.S. National Alzheimer's Plan has explicitly stated that palliative care needs to be incorporated throughout the course of caring for patients and families affected by dementia.

2.0 Rationale and Specific Aims

Aim 1: To test the effect of the IN-PEACE intervention on patients' neuropsychiatric symptoms (e.g., agitation/aggression, anxiety, repetitive behaviors). Mixed effects models will be used to compare repeated NPI-Q scores obtained at 3, 6, 9, 12, 15, 18, 21, and 24 months. Repeatedly measured NPI-Q scores will be the dependent variable in the model.

Aim 2: To test the effect of the IN-PEACE intervention on patients' overall symptom outcomes. Analyses in this aim will use repeatedly measured SM-EOLD scores over 24 months of follow-up as the dependent variable in the mixed effects model, similarly to the approach described for Aim 1.

Aim 3: To test the effect of the IN-PEACE intervention on caregivers' distress and mood. Aim 3 analyses will use repeatedly measured caregiver NPI-Q distress scores and caregiver PHQ-9 over 24 months of follow-up as the dependent variables in separate mixed effects models, similar to the approach for Aim 1.

Aim 4: Evaluate the effect of the IN-PEACE intervention on ER/hospital use. ER/hospitalization events will be obtained from accessing electronic medical records maintained by the Indiana Health Information Exchange (IHIE) and the Indiana Network for Patient Care (INPC). Poisson regression models will be used to compare rates of any ER/hospitalization event between the two groups while adjusting for dementia severity and significant baseline variables that differ between the two groups.

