8.0 Statistical Considerations

The proposed study is a RCT comparing the multi-component, supportive care intervention (IN-PEACE) to usual care. Primary and secondary outcomes will be collected at baseline, 3, 6, 9, 12, 15, 18, 21, and 24 months. A patient reaches study endpoint by either completing 24 months of follow-up or other conditions described in Subject tracking. We will compare baseline characteristics between the intervention group and the control group using two sample *t*-tests for continuous normally distributed variables, Wilcoxon test for continuous non-normal variables, or chi-square tests for categorical variables. Variables found to be significantly different at the α =0.05 level will be adjusted in the comparisons of all outcome variables.

Table 4: Power estimates for significant interactions between group and time in the mixed effect

models with 85 patients per group.

Outcome Measures	. Ou	d Change in tcome th interval)	Power			
	Intervention	Intervention Usual Care				
Aim 1: NPI-Q Severity	-0.45	0.2	80%			
Aim 2: SM-EOLD	1.31	0*	85%			
Aim 3a: Caregiver NPI-Q distress	-0.39	0.08	80%			
Aim 3b: Caregiver PHQ-9	-0.22	0.16	81%			

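### Aims 1–3 name no deciding contrast, form of time or fixed baseline term, and the only stated covariate rule leaves the collected baseline score to a 0.05 imbalance test

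*Combined protocol and SAP*

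**What the plan says.** Section 2.0, Aim 1: "Mixed effects models will be used to compare repeated NPI-Q scores obtained at 3, 6, 9, 12, 15, 18, 21, and 24 months", followed by "Repeatedly measured NPI-Q scores will be the dependent variable in the model". The visit list starts at month 3. Aim 2 uses its own scale "over 24 months of follow-up as the dependent variable in the mixed effects model, similarly to the approach described for Aim 1", and Aim 3 is described in the same way. None of the three names a group effect, a group-by-time term, a target visit or average, linear or categorical time, or a baseline term. Aim 4, by contrast, does name a fixed covariate: "adjusting for dementia severity and significant baseline variables that differ between the two groups".

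Section 8.0: "Primary and secondary outcomes will be collected at baseline, 3, 6, 9, 12, 15, 18, 21, and 24 months". The assessment schedule and the data-collection text in section 5.0 agree that month 0 is measured. The same paragraph of section 8.0 tests baseline characteristics between arms and says that those differing at the 0.05 "level will be adjusted in the comparisons of all outcome variables". It does not say whether an outcome's own month-0 score counts as a baseline characteristic.

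The group-by-time interaction appears only in the caption of Table 4: "Power estimates for significant interactions between group and time in the mixed effect". The rows are labelled by aim and give one expected change per interval in each arm, with 85 patients per group and power of 80–85%.

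**The concern.** Two things are left open.

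The first is the role of baseline. For a comparison of means, the outcome's own baseline score is usually the most useful covariate. A rule that admits it only after a significant imbalance leaves it out in about 95% of trials, and it lets the data choose the model. An imbalance just short of the cut-off stays uncorrected.

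The second is the deciding test. The text is compatible with a slope interaction over months 3–24, a slope interaction that includes month 0, categorical-time versions of either, or a group difference averaged over follow-up. These answer different questions. If benefit comes early and is then held, they can give opposite answers on the same data. Unless the choice is fixed before unblinding, a positive or negative report could depend on it.

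**Working it through.** **Inputs from the documents.** Table 4, Aim 1: −0.45 against 0.2 per interval, so a difference of 0.65; 85 per group; power 80%. The interval is read as the 3-month visit interval, so visits are t = 0 to 8.

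**Assumptions, because the documents give no SD or correlation.** Two-sided 0.05; complete data on 85 per arm; random intercept and slope; residual SD 2–5; intercept SD 3–5; intercept–slope correlation −0.3 to 0.3.

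**1. Table 4.** The implied slope SE is 0.65/(1.960 + 0.842) = 0.232, and the implied per-person slope SD is 0.232 × √(85/2) = 1.513 per interval. This returns 80% by construction, so Table 4 is neither confirmed nor contradicted. The slope variance is calibrated to it: random-slope variance = 1.513² − residual variance/Sxx, with Sxx = 42 (t = 1–8) or 60 (t = 0–8). That gives a random-slope SD of 1.30–1.49 and an outcome SD of 3.6–7.1 at baseline, rising to 11–14 at month 24.

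**2. How often the 0.05 rule acts.** For one score, 5%. For at least one of four, 1 − 0.95⁴ = 18.5% if independent.

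**3. What the rule costs a mean contrast.** Adjustment multiplies the variance by 1 − r², where r is the baseline–outcome correlation (assumed). Starting from 80% unadjusted power:

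| r | 1 − r² | 0.05 rule | Always adjust | Overall type I error under the rule |
|---|---|---|---|---|
| 0.3 | 0.91 | 80.5% | 83.6% | 4.8% |
| 0.5 | 0.75 | 81.1% | 89.9% | 4.3% |
| 0.7 | 0.51 | 82.0% | 97.5% | 3.6% |

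At r = 0.5 the rule recovers 1.1 of the 9.9 points available.

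**4. Imbalance just short of the cut-off.** This is 1.96 × baseline SD × √(2/85). With SD 3.6–7.1 it is 1.1–2.1 NPI-Q points. At zero intercept–slope correlation, the correlation between baseline and the month 3–24 average is 0.22–0.56. The expected carry-over into the unadjusted average is then 0.5–1.4 points, and the conditional false-positive rate is 7–15%, against 5% adjusted. For correlations of −0.3 to 0.3 the ranges are 0.2–2.0 points and 5–20%.

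**5. Benefit reached by month 3 and held.** Let the group difference be D at every visit from t = 1 to 8.
- Interaction over months 3–24: the slope of a constant is 0, and every visit's difference from month 3 is D − D = 0. The signal is exactly zero with linear or categorical time, whatever the SDs, and for all four Table 4 outcomes. Power equals the 5% error rate.
- Linear interaction with month 0 as a response and arm-specific means: slope = D × Σ(t − 4)/60 over t = 1–8 = 4D/60 = D/15. Take D = 4.5 × 0.65 = 2.925, the average over months 3–24 of Table 4's linear effect. The slope is 0.195, z = 0.195/0.232 = 0.84, and power is 13%. Calibrating with Sxx = 42 gives up to 14%.
- The same test with a common month-0 mean: 15–39% at zero correlation, and 5–67% over −0.3 to 0.3.
- Baseline-adjusted average over months 3–24: 74–82% at zero correlation, against 62–80% unadjusted.

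**6. Linear growth, the only effect the documents quantify.** At zero correlation: slope over months 3–24, 77–80%; slope with month 0 and arm-specific means, 80–83%; slope with a common month-0 mean, 80–86%; adjusted average, 74–82%. Compared with the common-mean slope test, the adjusted average loses about 0.3–4 points at correlation −0.3, up to about 7.5 at zero and up to about 12 at 0.3.

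**7. Sensitivity.** A different calibration used within-person correlation 0.3–0.7, random slopes making up 0–90% of slope variance, and 80% power for the month 0–24 slope. The held pattern again gave 5% and 13% for the two slope tests. The averaged contrast ranged more widely: 18–78% unadjusted and 43–79% adjusted.

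**The case against.** The strongest reply is that Table 4 settles the matter. It sits in the statistical section, refers to the mixed models, labels its rows by aim and gives one change per interval per arm, which points to a linear group-by-time test. Under linear growth the linear slope tests and the adjusted average have similar power at zero correlation, so the choice looks minor. Large divergence needs an early, held benefit, which the documents do not posit; they do not say when benefit should appear.

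Most of this stands. Table 4 is good evidence of intent, and the exact zero applies only if month 0 is left out of the response. But a power-table caption does not commit the analysis, the aim text never adopts it, and it does not say whether month 0 is a response.

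A reader might infer four stronger claims, which the documents do not support:
- That baseline can enter only through the 0.05 rule. Exclusion of month 0 is inferred from Aim 1's visit list and is not stated as a rule. The wording of Aims 2 and 3 could include month 0 as a response.
- That the 0.05 rule makes the trial's tests invalid. Overall type I error is not inflated; the 7–15% is conditional on a near-miss imbalance.
- That Table 4 is wrong. It cannot be checked without an SD and correlation.
- That an averaged contrast is simply better, or that fixing the role of baseline never costs power. Under linear growth the adjusted average can lose to the common-mean slope test. For a held benefit, the common-mean slope test can fall to 5%, below the 13–14% with arm-specific means.

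**Conclusion.** The point holds as a gap in specification, not an arithmetic error, and should be fixed. It has two parts.

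First, if the deciding test is a mean contrast, the 0.05 rule forfeits most of the precision available from a score that is already collected, and leaves near-significant imbalances uncorrected. The loss is roughly 3 to 15 points of power for baseline–outcome correlations of 0.3 to 0.7, starting from 80%.

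Second, if the deciding test is the interaction that Table 4 powers, the role of month 0 must be stated. Over months 3–24 alone, an early held benefit gives exactly zero signal, which needs no assumed SD or correlation. With month 0 as a response and arm-specific means, power for that pattern is still only about 13–14%.

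Every other figure rests on assumed SDs and correlations and is illustrative. The same concern extends to SM-EOLD, caregiver distress and PHQ if the similar approach in Aims 2 and 3 means the same model.

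**What to change.** 1. For the outcome's own baseline score, replace the 0.05 rule in section 8.0 by unconditional inclusion in every Aim 1–3 model. Use it as a covariate if the deciding test is a mean contrast, or as a month-0 response if it is a group-by-time interaction. A baseline covariate alone does not rescue an interaction fitted to months 3–24.
2. State in the aim text, before unblinding, which contrast decides and the form of time. Make Table 4 describe that contrast, with its SD, correlation and number of visits.

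The smallest change is to adopt Table 4's linear interaction with month 0 as a response, to say whether the month-0 mean is common to both arms, and to acknowledge that power for an early, held benefit may be low (13–14% with arm-specific means; 5–67% with a common mean, depending on the intercept–slope correlation). A baseline-adjusted average over months 3–24 is an option, not a correction. It is sensitive to an early benefit but can lose up to about 12 points under linear growth in the SD range used here, and more with larger SDs.

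The cost is wording and a re-run of Table 4. No new data are needed.

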3.0 Inclusion/Exclusion Criteria

We will recruit a total of 225 patient-caregiver dyads, randomizing 112 dyads each to the intervention and control (usual care) arms.

Eligibility criteria for patients include:

- age 65 or older
- community-dwelling in the Indianapolis metropolitan area (assisted living facility acceptable; long stay NH residents excluded);
- have an established diagnosis of dementia of any etiology as determined by memory care practice and confirmed by research team review of medical record;

- dementia in the moderate (FAST stage 5) to severe stage (FAST 6-7); and
- have a primary caregiver available and willing to serve as both an informant on the patient's status and as a subject him or herself.

Exclusion criteria for patients include:

- resident living in a nursing facility, Skilled Nursing Facility, Long Term Acute Care (LTC), Personal Care Home
- patient expressing dissent
- being diagnosed with a serious mental illness such as bipolar or schizophrenia
- Hospice enrollment (Addition IRB Approved: 5/13/2019)

Eligibility criteria for caregivers include:

- reside locally;
- English-speaking;
- live with patient or have at least 2 contacts per week on average with the patient (1 face-to-face);
- designation as the patient's primary caregiver; and
- has not been diagnosed with a serious mental illness such as bipolar or schizophrenia.

Recruitment

Dyads will be recruited from Indiana Discovery Network for Dementia (http://indydiscoverynetwork.org/) memory care practices in the Indianapolis area. Utilizing established memory care practices allows us to rely on their diagnostic assessment (confirmed by record review by research team) and to efficiently recruit eligible subjects. Our customary and successful recruitment methods utilize the Indiana Network for Patient Care (INPC) and the Indiana Health Information Exchange (IHIE) to identify potentially eligible patients with dementia based on ICD-9 and ICD-10 diagnostic codes and prescriptions for anti-dementia drugs in medical records. Memory care providers then help narrow the list of potential dyads to be approached and allow access to clinic schedules. Research assistants then arrange to meet dyads at a clinic appointment or offer a home visit to discuss the study.

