5.0 Study Procedures

Timeline

The study will take place over five years with a six month start-up time period. It will take 24 months to accrue the target sample size utilizing a rolling enrollment and intervention delivery process. Subjects receive the intervention for 24 months and the last outcome assessment is also at 24 months. In the final year of the study, in addition to completing analyses and preparation of manuscripts, we would plan a competitive renewal proposal to continue following the subjects in order to address aims relating to care in the last days/weeks of life, hospice referral, and resource utilization.

	YEAR 01		YEAR 02	YE	AR 03	YEAR 04		YEAR 05	
Start-up activities									
Subject accrual		rolling en							
		months	Intris						
Intervention		each dyad receives 24 months of the intervention							
Delivery									
Outcome		each dyad assessed at baseline, 3, 6, 9,12, 15, 18, 21,							
assessments		and 24 months							
Analysis;									
manuscripts									

Assessments: Measures and Schedule of Administration

Domain	Measure	Items	Schedule (months)									
Domain	IVICASUI C		0	3	6	9	12	15	18	21	24	EOL
Patient (PT) measu	res											
Patient related mea	sures assessed directly by research	assista	nt									
Cognition	MOQA	30	Х				Х				Х	
Patient related mea	sures obtained via caregiver (CG) in	terview	(proxy	y repo	ort)							
Neuropsychiatric Symptoms	Neuropsychiatric Inventory Questionnaire (NPI-Q) ⁹¹	12	Х	Х	Х	Х	Х	Х	Х	Х	Х	
Symptom Management	Symptom Management at the End of Life in Dementia (SM-EOLD) ⁹²	9	Х	Х	Х	Х	Х	Х	Х	Х	Х	Х
Comfort Assessment	Comfort Assessment in Dying with Dementia (CAD-EOLD) ⁹²	15										Х
Activities of Daily Living	Physical Self-Maintenance Scale ¹⁰⁶	13	Х	Х	X	Х	Х	X	X	X	Х	
Functional status	FAST staging ⁸⁰ (caregiver report, ADLs)		Х									
Medical comorbidity	Checklist of conditions ¹¹	10	Χ									
Caregiver measures												 
CG Distress from Neuropsychiatric Symptoms	Neuropsychiatric Inventory Questionnaire (NPI-Q) ⁹¹ (CG reaction portion of instrument)	12	Х	х	х	Х	Х	×	х	Х	х	
Depression (CG)	Patient Health Questionnaire (PHQ-8) ⁶⁵	9	Х	Х	Х	Х	Х	Х	Х	Х	Х	Х
Caregiver Strain	Caregiver Strain Index ¹⁰⁷	13	Х				Х				X	
Satisfaction with Care	Satisfaction with Care at the End of Life in Dementia (SWC-EOLD) ⁹²	10	Х	Х	Х	Х	Х	Х	Х	Х	Х	Х

Respondent Burden	Benefit and Burden Scale ¹⁰⁸	4		Χ	Х	Χ	Х	Х	Х	Х	Х	Х
Other data from CG	interview											

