Advance Care Planning (ACP)	Questions on specific directives	10	Х	Х	Х	Х	Х	Х	Х	Х	Х	
Hospice	Hospice utilization	4										Х
Socio-demographics (PT/CG)	age, race, sex, education, marital, job status, income	10	Х									
Medical Record Rev	riew and INPC/IHIE Data Stream											
Etiology of Dementia	Chart review	n/a	X									
ER/Hospitalizations	Health information exchange data	n/a					Х				Х	Х

Intervention

Intervention arm. Multi-disciplinary clinical team meetings with PI, co-investigators (MA, KK, SH, AMT), and care coordinators will be held weekly throughout the study. During these meetings, the team will review data from the baseline assessments to

- identify triggers for interventions,
- make protocol and other treatment recommendations, and
- communicate these to the care coordinator for dyads randomized to the intervention arm.

Caregivers will be contacted by the care coordinator within one week following the clinical team meeting or within ten days of the baseline assessment.

Care coordinators will initiate caregiver protocols to address unmet needs and individualized areas of focused care, overcoming barriers to provision of excellent palliative care. The assigned care coordinator will be the primary contact and will follow the dyad throughout the study with backup support and cross-coverage (i.e. social worker may call in RN for help with nursing issues and vice versa).

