Baseline and final outcome assessments will be done in person at the subjects' home or the memory care practice site. Other outcome assessments will be done by phone or in the home, based on caregiver preference. The outcome measures for both intervention and usual care groups will be collected at baseline and months 3, 6, 9, 12, 15, 18, 21, and 24 post-enrollment. Caregivers also will be interviewed 6 to 8 weeks after the patient's death if that occurs during the course of the study. Data will be collected by research assistants who have not been involved in the ongoing management of the patients and are blinded to dyad assignment to intervention or usual care arm.

Data obtained from the one-time qualitative interview will be audio-record and transcriptions will be used for data analysis using grounded theory.

6.0 Reporting of Adverse Events or Unanticipated Problems involving Risk to Participants or Others

The safety monitoring for this study will be the responsibility of the Principal Investigator ([name]), study biostatistician ([name]), and Safety Officer, who is external to Indiana University, and who are knowledgeable about dementia and older adults. Specifically, the Safety Officer will be selected based on the knowledge and experience in dementia, caregiving, palliative care, and clinical research studies. The Safety Officer, PI, Program Officer, and study biostatistician will meet by phone semi-

annually during active recruitment, data collection and analysis. Topics the group will review include: inclusion/exclusion criteria; participant accrual; and adherence and modifications to research protocols and procedures. Preliminary data trends on the primary and secondary outcomes will be discussed. In addition, the group will review procedures for protection of human subjects, including study withdrawals and adverse events reports and devise stopping rules, as applicable, based on potential harms and adverse events.

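### Aim 4's Poisson regression makes no provision for variance that differs from the mean: intervals are too narrow for overdispersed counts and too wide if the outcome is at least one event

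*Combined protocol and SAP*

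**What the plan says.** The Aim 4 paragraph in section 2.0 is the only text on this model. It states that "Poisson regression models will be used to compare rates of any ER/hospitalization event between the two groups", with adjustment for dementia severity and for baseline variables on which the arms differ significantly. On the data it says that "ER/hospitalization events will be obtained from accessing electronic medical records". The assessments table in section 5.0 lists the source as "Health information exchange data", at months 12 and 24 and at end of life.

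Section 8.0 adds only the general covariate rule: baseline variables that differ between arms at the 0.05 level are adjusted for in every outcome comparison. Table 4 gives power for Aims 1 to 3 and has no row for Aim 4. No section mentions overdispersion, a scale parameter, robust standard errors, quasi-Poisson or negative binomial models, a dispersion check or a person-time offset.

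Three other places bear on the point:
- **Population (section 3.0).** Patients must "have an established diagnosis of dementia of any etiology" and may be at FAST stage 5, 6 or 7. The trial is "randomizing 112 dyads each to the intervention and control (usual care) arms".
- **Comorbidity (section 5.0).** It is recorded at baseline ("Checklist of conditions"), but enters the model only if the arms happen to differ on it.
- **Follow-up (sections 5.0 and 8.0).** Caregivers are interviewed after the patient's "death if that occurs during the course of the study", and "A patient reaches study endpoint by either completing 24 months of follow-up or other conditions described in Subject tracking". Observation time can therefore differ between patients.

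**The concern.** Ordinary Poisson inference takes the variance of each patient's count to equal its mean. Hospital and emergency use usually departs from this when patients differ in underlying risk and the model does not capture the differences. Here severity is in the model, but etiology and comorbidity enter only through chance imbalance, a rule that does not respond to how strongly they predict events. Unequal follow-up adds further variation if there is no offset.

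If the counts are overdispersed, the standard error of the rate ratio is too small. A difference in ER and hospital use could then be declared when the intervention has no effect on it.

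The wording also leaves the outcome open. The plural events, the word rates and the choice of Poisson all favour a count. The phrase about any event could instead mean that a patient had at least one. For a yes/no outcome the variance is below the mean, so the model-based error runs the other way: the intervals are too wide and real effects are harder to detect.

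**Working it through.** The documents give no event rate, dispersion, effect size, power or significance level for Aim 4, so there is no figure of the plan's to reproduce. The 0.05 in section 8.0 applies only to selecting baseline covariates.

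**Inputs from the documents.** 112 dyads per arm (section 3.0); 85 per group (Table 4, for Aims 1 to 3); severity adjustment (Aim 4).

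**Assumptions.** A two-sided 5% test; the variance-to-mean ratio φ; the mean number of events per patient over 24 months.

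**Step 1: closed form for a count.** If the variance is φ times the mean, the model-based standard error is too small by a factor √φ. The actual type I error is then 2 × [1 − Φ(1.96/√φ)], and a correct interval is √φ times as wide on the log scale.

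| φ | 1.96/√φ | Type I error | Coverage of nominal 95% interval | Correct width / model-based width |
|---|---|---|---|---|
| 1 | 1.96 | 5.0% | 95.0% | 1.00 |
| 1.5 | 1.60 | 11.0% | 89.1% | 1.22 |
| 2 | 1.39 | 16.6% | 83.4% | 1.41 |
| 3 | 1.13 | 25.8% | 74.2% | 1.73 |

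**Step 2: how much patient variation these ratios need.** When patients' own event rates vary with coefficient of variation CV, φ = 1 + mean × CV², so CV = √((φ − 1)/mean). For φ = 1.5, 2 and 3 this gives 0.50, 0.71 and 1.00 at a mean of 2 events, and 0.71, 1.00 and 1.41 at a mean of 1. The documents do not say where this population lies.

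**Step 3: simulation of the adjusted model under no effect.** Gamma-Poisson counts, 112 per arm, 20,000 runs per cell. Assumed: half of each arm at FAST 6-7 with a 1.5-fold event rate, and 24% of patients with follow-up ending uniformly before 24 months. The 24% is 1 − 85/112 = 0.241; the documents do not explain that gap. The fitted model was Poisson on group and FAST stratum with a log follow-up offset.

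| φ | Model-based, mean 2 | Robust, mean 2 | Model-based, mean 1 | Robust, mean 1 |
|---|---|---|---|---|
| 1 | 4.9% | 5.0% | 4.8% | 4.9% |
| 1.5 | 10.4% | 5.1% | 10.8% | 5.5% |
| 2 | 16.7% | 5.4% | 16.4% | 5.4% |
| 3 | 25.7% | 5.5% | 25.5% | 5.9% |

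**Step 4: a separate, simpler simulation.** Unadjusted comparison with equal follow-up, 85 or 112 per arm, means of 1 to 3 and φ from 1 to 4. Model-based type I error was 16.0% to 16.7% at φ = 2 and 25.2% to 25.9% at φ = 3. Over all settings, robust variance gave 5.1% to 5.9% and Pearson-scaled (quasi-Poisson) variance gave 4.9% to 5.4%.

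**Step 5: the at-least-one-event reading.** For a 0/1 outcome with risk p, the variance-to-mean ratio is 1 − p, so the same formula applies with φ = 1 − p. At assumed risks of 30%, 50% and 70% it gives 1.9%, 0.6% and 0.03%. Simulation gave about 1.7%, 0.5% and under 0.1%. Robust variance gave 4.2% to 5.5%.

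**The case against.** The plan names a model family, not a software call. Aims 1 to 3 likewise say only that mixed models will be used, without a covariance structure. Nothing states that model-based standard errors will be reported or that dispersion will go unchecked, and the subject-tracking text to which section 8.0 refers is not in the document as available. On this view the point is thin specification of an aim that has no power statement. That stands in part: the documents do not show that an analyst would ignore overdispersion. It does not dispose of the point, because the method as written has no variance provision, and choosing one after the results are seen leaves discretion that a sentence now would remove.

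A reader might infer that the Aim 4 test will reject 11% to 26% of the time under no effect. The documents do not support that. Those figures follow from assumed ratios; a population that is mixed in etiology, stage and comorbidity makes overdispersion plausible but does not measure it. At φ = 1 there is no distortion, and on the yes/no reading the error is in the other direction.

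A reader might also infer that robust variance is the only sound remedy, or that it restores exactly 5%. Neither holds. The highest robust cell, 0.0587, lies about 6 Monte Carlo standard errors above 0.05 (√(0.05 × 0.95/20,000) = 0.0015), a small but real excess. Quasi-Poisson variance did at least as well for a count.

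Finally, rates under a Poisson model ordinarily imply person-time, so the missing offset is a matter of making it explicit. The 24% early-ending figure comes from a table on other aims and need not apply to health-exchange data; it does not drive the result.

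**Conclusion.** The point holds in conditional form. As written, Aim 4 relies on a variance that is correct only for a count whose variance equals its mean. It is too small for overdispersed counts and too large for an at-least-one-event outcome. The count is the more natural reading and overdispersion is plausible, so false-positive findings are the likelier risk, but the documents settle neither the outcome nor the dispersion.

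The size is illustrative. It rests on an assumed two-sided 5% level and assumed ratios of 1 to 3, which give a type I error from 5% (no distortion) to about 26%. Confidence is medium for that reason. The change is worth making because a cheap method exists that is valid under both readings.

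**What to change.** In the Aim 4 sentence, specify Poisson regression with robust (sandwich) variance as the primary analysis and keep the planned dementia-severity adjustment. If the outcome is a count, a Pearson-scaled quasi-Poisson variance is an acceptable alternative; name one in advance.

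In the same place, state whether the outcome is the number of ER/hospitalization events or at least one event. For a count, state that log observed follow-up time is the offset.

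The cost is a sentence or two of wording and a variance option in the model call, with no new data. Count intervals may become wider. No stated power or sample size changes, because Table 4 does not cover Aim 4.

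### Aim 4 does not plan to adjust for ER/hospital use before randomisation, and the plan's own passages disagree on whether a baseline value is collected

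*Combined protocol and SAP*

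**What the plan says.** **Outcome and model.** Section 2.0 (Aim 4) takes the outcome from two record sources, the INPC and the state exchange: "ER/hospitalization events will be obtained from accessing electronic medical records maintained by the Indiana Health Information Exchange (IHIE"). The analysis is described thus: "Poisson regression models will be used to compare rates of any ER/hospitalization event between the two groups". On covariates, the comparison is made "while adjusting for dementia severity and significant baseline variables that differ between the two groups".

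**Covariate rule.** Section 8.0 sets the threshold for all outcomes: "Variables found to be significantly different at the α =0.05 level will be adjusted in the comparisons of all outcome variables".

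**Schedule.** In the section 5.0 assessments table, the ER/Hospitalizations row gives its measure as "Health information exchange data". It is marked at months 12, 24 and EOL, and the month-0 cell is blank. The outcomes of Aims 1 to 3 (NPI-Q, SM-EOLD, caregiver NPI-Q distress and the caregiver PHQ) all have a month-0 mark.

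**General statements on timing.** Section 8.0 says: "Primary and secondary outcomes will be collected at baseline, 3, 6, 9, 12, 15, 18, 21, and 24 months". The Data Collection part of section 5.0 gives the same list of visits: "The outcome measures for both intervention and usual care groups will be collected at baseline and months 3, 6, 9, 12, 15, 18, 21, and" the final visit.

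**Other use of the same source.** Section 3.0 (Recruitment) says the INPC and IHIE are used "to identify potentially eligible patients with dementia based on ICD-9 and ICD-10 diagnostic codes and prescriptions for anti-dementia drugs in medical records".

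**The concern.** ER and hospital use usually varies widely between patients and tends to persist within a patient. With about 112 dyads per arm, a few habitual high users falling in one arm by chance can move the rate ratio noticeably. The usual remedy is to put prior use in the model. Aim 4 does not do so. Its outcome has no month-0 mark in the schedule, and no other listed baseline item records prior use; the nearest is a 10-item comorbidity checklist.

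At stake is the width of the Aim 4 interval, and a direct view of whether the arms began with similar use. Aim 4 also has no power statement: Table 4 covers Aims 1, 2, 3a and 3b only. Precision that costs little to obtain is therefore worth having.

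**Working it through.** **1. Is a baseline value planned?** The sources side by side:

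| Place | Baseline ER/hospital use |
|---|---|
| 5.0, ER/Hospitalizations row | Not marked (12, 24, EOL only) |
| 5.0, Data Collection | Outcome measures at baseline, in a paragraph about in-person and telephone assessments |
| 8.0 | Primary and secondary outcomes at baseline; the documents do not say which class ER/hospital use belongs to |
| 2.0, Aim 4 | Not mentioned |

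The blank cell does not look like a table-reading fault. The MOQA row has the same 12-month spacing and does carry a month-0 mark. The row and the general statements therefore disagree, and none of them says how far back an extraction reaches.

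**2. Would prior use enter the model if it were recorded?** Dementia severity always enters. Anything else enters only if the arms differ at 0.05. Under randomisation, a correctly sized test does that about 5% of the time for any one variable. In the other 95% or so, the predictive value of prior use would go unused.

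**3. Size of the gain.** The plan gives no event rate, rate ratio, dispersion or power for Aim 4, so there is no stated figure to reproduce. Everything below is an assumption.

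Let r be the correlation between prior and follow-up use on the model scale. Residual variance factor = 1 − r². Equivalent sample gain = 1/(1 − r²) − 1.

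| r | 1 − r² | Variance reduction | Equivalent sample gain |
|---|---|---|---|
| 0.2 | 0.96 | 4% | 4% |
| 0.3 | 0.91 | 9% | 10% |
| 0.4 | 0.84 | 16% | 19% |
| 0.5 | 0.75 | 25% | 33% |

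Here r must refer to total outcome variance left after FAST stratum. If it describes only the stable between-patient component, the gain is smaller, because Poisson event noise remains.

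**4. Simulation check.** Inputs, all assumed apart from the 112 per arm: rate ratio 0.7 (log RR −0.357); gamma frailty shared between a 12-month prior period and a full 24 months of follow-up; no deaths or dropout; Poisson regression with robust standard errors; covariate log(prior count + 0.5); 800 runs per scenario.

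| Control mean over 24 months, frailty variance | SD of log RR, without → with | Variance ratio | Power, without → with |
|---|---|---|---|
| 2, 1.0 | 0.172 → 0.144 | (0.144/0.172)² = 0.70 | 59% → 72% |
| 1, 1.0 | 0.205 → 0.190 | (0.190/0.205)² = 0.86 | 45% → 51% |
| 2, 0.5 | 0.135 → 0.128 | (0.128/0.135)² = 0.90 | 72% → 79% |

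Mean log RR was about −0.36 with and without the covariate in every scenario. The gain is in precision, and there was no bias to remove. The first scenario gives a 30% reduction, above the range in step 3. It assumes perfectly stable frailty and complete follow-up, so it is a favourable case.

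**The case against.** The strongest reply is that this is a preference about precision and not an error. Dyads are randomised with stratification by FAST, and Aim 4 adjusts for dementia severity. Omitting a further predictor leaves the comparison valid, and no stated power depends on it. That stands, and it sets the weight of the point.

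It can also be said that section 8.0 already promises baseline outcomes and adjustment for those that differ. If ER/hospital use counts as a secondary outcome, a baseline value is planned. This stands in part: absence cannot be asserted from the schedule row alone. But section 8.0 contradicts the row, gives no look-back period, and would admit prior use only after a significant imbalance.

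Three stronger readings are tempting, and the documents do not support them:

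- **That Aim 4 cannot adjust for prior use.** A mark in the schedule shows when records are pulled, not how far back the pull reaches. A month-12 extraction could include the period before enrollment. The text supports only that adjustment is not planned.
- **That the exchange certainly holds prior use for everyone.** Section 3.0 describes searches for diagnosis codes and prescriptions, not encounters. Section 5.0 is silent on coverage, and patients may self-refer, so they need not have entered through that search. Availability is a reasonable inference, not a stated fact.
- **That prior use would reveal whether a patient's hospitals report to the exchange.** A zero count cannot separate a non-user from a patient whose hospitals do not report.

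Finally, the size rests on an assumed correlation, and the simulation ignores death and dropout in a population with moderate to severe dementia. Table 4 itself works with 85 per group against 112 randomised, 24% fewer (1 − 85/112). The gain should be read as a range and not as a promise.

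**Conclusion.** The point holds as an inexpensive improvement, together with an inconsistency that needs correcting. Aim 4 does not prespecify adjustment for ER/hospital use before randomisation, the schedule and the general text disagree on baseline collection, and no look-back is defined. The consequence is a wider interval than necessary, not a biased rate ratio. For an assumed r of 0.2 to 0.5, residual variance would fall by about 4% to 25%. The assumed simulation scenarios gave 6 to 13 points of power with complete follow-up. Both would shrink with shortened follow-up, weaker persistence of use, or incomplete prior records.

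**What to change.** 1. Reconcile the ER/Hospitalizations row with the Data Collection text in section 5.0 and the timing sentence in section 8.0. State that this outcome comes from record extraction on its own timetable, and whether a baseline value is included.
2. In the planned INPC/IHIE extraction, include ER visits and hospitalizations over a defined look-back, for example the 12 months before randomisation, and mark month 0 in the row.
3. In Aim 4, prespecify that count, for example as log(count + 1), as a covariate alongside FAST stratum, whatever the baseline test shows. Do this before outcomes are analysed by arm.
4. State how patients with incomplete prior records, such as some self-referrals, will be handled. Do not treat a zero count as evidence about hospital reporting.

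Cost: a longer window in a data pull already planned, one model covariate, and a check that the records authorisation covers the look-back. No additional visits, staff or patients are needed.
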